## **Revision History**

### **Version 1.1 to 1.2**

1. Updated planned software from SAS to Python and related statistical packages (section 2.6).
2. Updated document ownership from [REDACTED] to Romark Institute for Medical Research.

### **Version 1.0 to 1.1**

1. Wording of futility analysis purpose in Section 2.4 clarified.
2. Risk differences added to primary efficacy endpoint.
3. Section 2.2.2 Sex, Age, and Race subgroup analyses for primary efficacy endpoint added.
4. Sensitivity analyses added for missing values of primary efficacy variable.

## Abbreviations and acronyms

---

AE	Adverse Event
ARI	Acute Respiratory Illness
ATC	Anatomic Therapeutic Chemical
CDER	Center for Drug Evaluation and Research
COVID-19	Novel Corona Virus Infectious Disease, 2019
CMH	Cochran-Mantel-Haenszel Chi-square Test
FDA	US Food and Drug Administration
IAP	Interim Analysis Plan
LTCF	Long Term Care Facility
NTZ	Nitazoxanide
RT-PCR	Reverse Transcriptase-Polymerase Chain Reaction
SARS-CoV-2	Severe Acute Respiratory Syndrome-Corona Virus 2, the pathogen causing COVID-19
TEAE	Treatment Emergent Adverse Event
VRI	Viral Respiratory Illness
WHO	World Health Organization

---

## 1.0 Synopsis of Study Design Procedures

### 1.1 Design and Treatment

This is a multi-center, randomized, double-blind, placebo-controlled trial to assess the safety and efficacy of Nitazoxanide (NTZ) for post-exposure prophylaxis of COVID-19, the viral respiratory disease caused by the novel coronavirus SARS-CoV-2 and other viral respiratory illnesses (VRI) in residents of long-term care facilities (LTCF) aged 65 years and over.

Participants will be randomized (1:1) within LTCF (i.e., within strata) to one of

- Group I (NTZ)—Two 300 mg NTZ tablets orally b.i.d. (twice daily) for six weeks;
- Group II (Placebo)—Two placebo tablets b.i.d. (twice daily) for six weeks.

All participants will receive a B-complex vitamin (██████████) twice daily to mask potential chromaturia that may be associated with NTZ.

### 1.2 Study Procedures

#### Screening

Patients will be screened from Study Day -90 to Study Day 1. After giving informed consent, the subject will be assigned a subject number and complete the following procedures:

1. Complete medical history.
2. Physical examination including body weight and vital signs (blood pressure, pulse, respiratory rate and body temperature).
3. Collection of demographic information and smoking history.
4. Evaluation according to eligibility (inclusion and exclusion) criteria.

The information collected during the screening period must be current through the time of randomization.

#### Baseline

At Baseline (Study Day 1, which may be the same day as the screening evaluation) the subject will be randomized to Group I or Group II and complete the following procedures:

1. Collection of two nasopharyngeal swabs (one from each nostril) using nylon flocked dry swabs for RT-PCR.
2. Collection of blood sample for laboratory safety tests and anti-SARS-CoV-2 antibodies.

3. Collection of a urine sample for routine urinalysis (appearance, glucose, protein and blood).
4. Review and recording of any concomitant medications.
5. Completion of baseline electronic symptom diary entries.
6. Randomization and dispensing of study medication (medication assigned in sequential order). Subjects will be considered enrolled in the study upon the randomized assignment to a treatment group.
7. Administration of the first dose of study medication with food (< 1 hour after food intake) and a B complex vitamin (██████████) under observation of Investigator or a member of Investigator's staff, and entry in the medication administration record.
8. The subject will be instructed regarding the administration of study medication, completion of the electronic subject diary, use of birth control, follow-up visits at weeks 1, 3, 6, 8, and on seeking emergency medical care or contacting the study physician or nurse under specific conditions.

CONTACT STUDY PHYSICIAN, IF:

- Trouble breathing including shortness of breath
- Severe headache, stiff neck, confusion, or excessive somnolence
- If fever ( $\geq 99^{\circ}\text{F}$  or  $\geq 37.2^{\circ}\text{C}$ ) returns after being absent for 24 hours
- Increased difficulty breathing
- Wheezing develops
- New pain develops or pain localizes to one area, such as an ear, the throat, the chest, or the sinuses
- Symptoms become more severe or frequent
- Symptoms recur or any difficulty breathing following 5-10 days resolution of illness
- An allergic-like reaction occurs or is suspected
- Abnormal behavior

### Study Weeks 1 through 6 (Daily)

A caregiver will record the time of each study medication intake. Once daily, the caregiver will (i) inquire regarding the health of the subject, (ii) record any concomitant medications, and (iii) ask the subject once daily, "do you feel like you have symptoms of a cold or flu?" If the subject responds "yes", the caregiver will have the subject complete a FLU-PRO© diary to evaluate the subject's symptoms.

If the subject reports (i) at least one of the Lower Respiratory Symptoms presented in Text Table 1 below or (ii) at least one symptom from each of the Upper Respiratory Symptoms and Systemic Symptoms categories presented in Text Table 1 below, the subject will then contact the study physician to complete a “Suspected ARI Visit” with the procedures provided below.

**Table 1: Clinical Illness Required for Diagnosis of ARI (adapted from Yu et al. 2020)**

Upper Respiratory Symptoms	Lower Respiratory Symptoms	Systemic Symptoms

 
• Nasal congestion/rhinorrhea (runny or dripping nose, congested or stuffy nose, head congestion, sinus pressure)
 
• Sore throat (sore or painful throat)
 
	
 
• Cough (coughing, chest congestion, chest tightness, dry or hacking cough, wet or loose cough)
 
• Dyspnea (shortness of breath)
 
• Sputum (coughing up sputum or phlegm)
 
• Wheezing
 
	
 
• Myalgias or arthralgias (body aches or pains)
 
• Fatigue (weak or tired, sleeping more than usual)
 
• Headache
 
• Decreased appetite (lack of appetite, did not feel like eating)
 
• Feverishness (felt hot, chills or shivering, felt cold, sweating)
 

 Suspected ARI requires self-reporting of any Lower Respiratory Symptom, or at least one Upper Respiratory Symptom together with one Systemic Symptom.

 Lay language used in the FLU-PRO® questionnaire is presented in parentheses.

### Suspected ARI Visit

Subjects reporting any lower respiratory symptom or at least one upper respiratory symptom and one systemic symptom are considered to have a suspected acute respiratory illness (ARI) and will complete the following procedures at an unscheduled Suspected ARI Visit.

1. Physical examination as warranted by the Investigator for any change from baseline.
2. Body weight and collection of vital signs to include blood pressure, pulse, respiratory rate and body temperature.
3. Collect two nasopharyngeal swabs using nylon flocked dry swabs for RT-PCR at the Suspected ARI Visit.
4. Collect two nasopharyngeal swabs 24 to 36 hours later, and then again 4 to 5 days later.

5. The subject will complete a FLU-PRO® symptom diary daily until he/she responds "yes" to the FLU-PRO® question, "Have you returned to your usual health?" for 3 consecutive days or until the Week 6 Visit, whichever occurs first. The daily FLU-PRO® diary will be completed between 4:00 pm and 8:00 pm. A caregiver may assist the subject with completing the diary if necessary.
6. Review and recording of concomitant medications.
7. Review and recording of adverse events/side effects.
8. Laboratory investigations for safety may be performed as warranted based upon the Investigator's judgment.
9. Subjects testing positive for a respiratory virus by RT-PCR may receive standard of care as clinically warranted by the Investigator.

Regardless of symptoms or laboratory data, the subject will continue treatment until the 6-week treatment period has ended.

### **Week 1, Week 3 and Week 6 Evaluations ( $\pm$ 2 days)**

Study personnel (physician, nurse, or other study personnel) will visit each subject at Week 3 and Week 6 and performing the following procedures:

1. Physical examination as warranted by the Investigator for any change from baseline.
2. Body weight and collection of vital signs to include blood pressure, pulse, respiratory rate and body temperature.
3. Collection of blood sample for laboratory safety tests, pharmacokinetics (pre-dose) and anti-SARs-CoV-2 antibodies (antibody testing at Week 6 visit only).
4. Collection of urine sample for routine urinalysis.
5. Review of compliance with study medication, collection of medication bottle with any unused medications (Week 6 visit only), and completion of the pill count log form.
6. Review and recording of concomitant medications.
7. Review and recording of adverse events/side effects and complications. Note that all adverse events and complications must be followed until their resolution or stabilization even beyond the 8-week study period.

### **Week 8 Evaluation ( $\pm$ 7 days)**

Study personnel (physician, nurse, or other study personnel) will visit each subject at Week 3 and Week 6 and performing the following procedures:

1. Physical examination as warranted by the Investigator for any change from baseline.
2. Collection of blood sample for anti-SARs-CoV-2 antibodies.

3. Review and recording of concomitant medications.
4. Review and recording of adverse events/side effects and complications. Note that all adverse events and complications must be followed until their resolution or stabilization even beyond the 8-week study period.
5. Document any infections diagnosed during the follow-up period.

### Other Unscheduled Visits

Subjects requiring an unscheduled visit due to worsening symptoms or adverse events will be evaluated at the discretion of the Investigator as is medically warranted. Tests and/ or procedures performed at this visit may include, but are not limited to, the following:

1. Physical examination as warranted by the Investigator for any change from baseline.
2. Body weight and collection of vital signs to include blood pressure, pulse, respiratory rate and body temperature.
3. Collection of two nasopharyngeal swabs using nylon flocked dry swabs for RT-PCR.
4. Collection of blood sample for laboratory safety tests.
5. Collection of urine sample for routine urinalysis.
6. Review of compliance with study medication.
7. Review and recording of concomitant medications.
8. Review and recording of adverse events/side effects.

### 1.3 Sample Size

Recent reports of COVID-19 in long-term care facilities in the United States have suggested a high rate of transmission of the SARS-CoV-2 virus, but infection control procedures may significantly decrease transmission (McMichael et al. 2020, Kimball et al. 2020). A recent study of 264 elderly volunteers ( $\geq 65$  years of age) reported 1.6 respiratory tract infections (not laboratory-confirmed) per person-year indicating approximately a 20% probability of respiratory tract infection over a given 6-week period (Mannick et. al, 2018). Infection control procedures in place during the period covered by this clinical trial are also expected to reduce the transmission of other respiratory viruses.

For purposes of calculating sample size, we assume that the proportion of subjects experiencing COVID-19 over a 6-week period is 5%, the proportion of subjects experiencing any VRI is 10%, and that effective prophylaxis will reduce the rate of COVID-19 and other VRIs by 80%.

A Cochran-Mantel-Haenszel (CMH) chi-square test stratifying by 20 LTCFs will have 87.1% statistical power to detect the difference between 5% and 1% rates of occurrence of COVID-19 across all strata at a two-sided alpha of 0.047 with a total sample size of 800, allocated equally to strata (LTCFs) and treatment groups within strata. The statistical

power remains >87% when the number of LTCFs is 5, 10, 16 or 20. The CMH chi-square test has 91% power to detect the difference between 10% and 2% rates of occurrence of VRIs over all strata at a two-sided alpha of 0.001 with 800 subjects allocated equally to 20 LTCFs. Both tests are insensitive to stratum size. Varying the number of subjects per stratum (LTCF) between a minimum of 8 to a maximum of 80 while holding both the effect size and total sample constant results in changes in the third significant figure of the test's power.

A sample size of 800 subjects (400 per treatment group) was selected.

## 2.0 Data Analysis Considerations

### 2.1 Types of Analyses

Data analyses will consist of analyzing patient characteristics, safety, and efficacy data.

### 2.2 Analysis Populations

#### 2.2.1 Population Definitions

Subjects will be considered enrolled in the study upon completion of the baseline procedures. The following analysis populations will be used in the study.

- **Safety Population** – the safety population includes all patients who are enrolled in the study and that have received at least one dose of the assigned treatment arm (NTZ or placebo)
- **Intention to Treat Population (ITT)** – the ITT population includes all patients in the safety population who did not have a laboratory detected respiratory virus infection at the baseline visit.

The safety population will be used for all safety analyses. The ITT population will be the primary population for all efficacy analyses.

Data listings displaying the patients excluded from each population will be created. These listings will be relative to all patients enrolled in the study.

#### 2.2.2 Subgroup Definitions

Safety analyses will be grouped by treatment received. The primary efficacy analysis will be grouped by sex (male/female), age (65 to 79 years, 80 years and over), and race (white/non-white).

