4.1. Inclusion Criteria

1. Male and female residents of LTCFs at least 55 years of age.
2. Willing and able to provide written informed consent and comply with the requirements of the protocol.
3. At least one symptomatic laboratory-confirmed COVID-19 illness identified among residents or staff of the LTCF within 10 days prior to randomization.

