## 3.0 Analysis of Baseline Patient Characteristics

Baseline and demographic characteristics of the safety population will be summarized. Continuous variables (age, baseline height, baseline weight) will be summarized via mean, standard deviation, minimum, median, maximum, and number of non-missing responses. Categorical variables (gender, race, and ethnicity) will be summarized via counts and percentages.

A detailed listing of baseline data for each patient in the safety population will also be provided as shown in Appendix B.

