## 4.2 Efficacy Analysis

### 4.2.1 Primary Efficacy Variables

The study has two primary efficacy endpoints: reduction in symptomatic COVID-19 disease and reduction in all VRI. The study-wise  $\alpha$  level is set at 0.05, allocated with 0.049 to the COVID-19 endpoint and 0.001 to the all VRI endpoint. See Section 2.4 for details on how the study- wise  $\alpha$  level will be allocated to the interim and final analyses. For each endpoint, the following hypotheses will be tested

$$H_0: p_1 = p_2$$

$$H_1: p_1 \neq p_2,$$

here,  $p_1$  represents the probability of symptomatic disease (either COVID-19 or VRI) in the NTZ treatment group and  $p_2$  represents the probability of symptomatic disease in the placebo group.

The proportion of subjects experiencing symptomatic COVID-19 disease in the NTZ treatment group will be compared to the similar proportion in the placebo group using a two-sided CMH test with continuity correction at  $\alpha=0.047$ . The test will be stratified by LTCF. The contingency tables will be provided with rates relative to the treatment margins. A 95% confidence interval for the odds ratio of symptomatic COVID-19 infection in the NTZ group relative to the placebo group will be provided. The risk difference for the treatment groups and a 95% confidence interval for the difference will be provided.

The proportion of subjects experiencing symptomatic VRI infections in the NTZ treatment group will be compared to the similar proportion in the placebo group using a two-sided CMH test, stratified by LTCF with continuity correction at  $\alpha=0.001$ . The contingency tables will be provided with rates relative to the treatment margins. A 95% confidence interval for the odds ratio of symptomatic VRI in the NTZ group relative to the placebo group will be provided. The risk difference for the treatment groups and a 95% confidence interval for the difference will be provided.

CMH analyses of symptomatic COVID-19 disease and symptomatic VRI will be repeated with subjects divided by sex (female or male), age (65- to 79 years or 80 years and over), and race (white or non-white). Estimates and confidence intervals for the odds ratio and relative risk differences will be provided.

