## 8.0 List of Analysis Tables, Figures and Listings

Table No.	Table Title
14.1.1.1	Subject Disposition Summary by Treatment and Overall (All Subjects)
14.1.2.1	Summary of Major Protocol Deviations (Safety Population)
14.1.2.2	Summary of Minor Protocol Deviations (Safety Population)
14.1.3.1	Summary of Demographic Categorical Variables by Treatment and Stratum (Safety Population)
14.1.3.2	Summary of Demographic Quantitative Variables by Treatment and Stratum (Safety Population)
14.1.4	Summary of Treatment Compliance (Safety Population)
14.2.1.1	Cochran-Mantel-Haenszel Test Results: Symptomatic COVID-19 Subject Status (ITT Population)
14.2.1.2	Cochran-Mantel-Haenszel Test Results: Symptomatic VRI Subject Status (ITT Population)
14.2.1.3	Cochran-Mantel-Haenszel Test Results: Symptomatic COVID-19 Subject Status with Best-Case and Worst-Case Analysis of Missing Data (ITT Population)
14.2.1.4	Cochran-Mantel-Haenszel Test Results: Symptomatic VRI Subject Status with Best-Case and Worst-Case Analysis of Missing Data (ITT Population)
14.2.1.5	Cochran-Mantel-Haenszel Test Results: Symptomatic COVID-19 Subject Status with Tipping Point Analysis of Missing Data (ITT Population)
14.2.1.6	Cochran-Mantel-Haenszel Test Results: Symptomatic VRI Subject Status with Best-Tipping Point Analysis of Missing Data (ITT Population)
14.2.1.7	Cochran-Mantel-Haenszel Test Results by Sex: Symptomatic COVID-19 Subject Status (ITT Population)
14.2.1.8	Cochran-Mantel-Haenszel Test Results by Sex: Symptomatic VRI Subject Status (ITT Population)
14.2.1.9	Cochran-Mantel-Haenszel Test Results by Age Group: Symptomatic COVID-19 Subject Status (ITT Population)
14.2.1.10	Cochran-Mantel-Haenszel Test Results by Age Group: Symptomatic VRI Subject Status (ITT Population)
14.2.1.11	Cochran-Mantel-Haenszel Test Results by Race: Symptomatic COVID-19 Subject Status (ITT Population)
14.2.1.12	Cochran-Mantel-Haenszel Test Results by Race: Symptomatic VRI Subject Status (ITT Population)
14.2.2.1	Cochran-Mantel-Haenszel Test Results: COVID-19 Related Hospitalization Status (ITT Population)

Table No.	Table Title
14.2.2.2	Cochran-Mantel-Haenszel Test Results: COVID-19 Related Mortality Subject Status (ITT Population)
14.2.2.3	Cochran-Mantel-Haenszel Test Results: COVID-19 Antibody Test Subject Status (ITT Population)
14.2.3.1	Cochran-Mantel-Haenszel Test Results: VRI Related Hospitalization Subject Status (ITT Population)

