14.2.3.2	Cochran-Mantel-Haenszel Test Results: VRI Related Mortality Subject Status (ITT Population)
14.2.3.3	Cochran-Mantel-Haenszel Test Results: ARI Subject Status (ITT Population)
14.2.3.4	Cochran-Mantel-Haenszel Test Results: ARI Related Hospitalization Subject Status (ITT Population)
14.2.3.5	Cochran-Mantel-Haenszel Test Results: ARI Related Mortality Subject Status (ITT Population)
14.3.1.1	Treatment Emergent Adverse Events Summary: Total AE, Toxicity Grade, Relationship to Treatment, Serious AEs by Treatment (Safety Population)
14.3.1.2	Treatment Emergent Adverse Events by System Organ Class, Preferred Term, and Treatment (Safety Population)
14.3.1.3	Treatment Emergent Adverse Events by System Organ Class, Preferred Term, Treatment, and Toxicity Grade (Safety Population)
14.3.1.4	Treatment Emergent Adverse Events by System Organ Class, Preferred Term, Treatment, and Relationship to Treatment (Safety Population)
14.3.1.5	Treatment Emergent Serious Adverse Events by System Organ Class, Preferred Term, and Treatment (Safety Population)
14.3.2.1	Clinical Laboratory Summary Statistics: Hematology (Safety Population)
14.3.2.2	Clinical Laboratory Shift Tables: Hematology (Safety Population)
14.3.3.1	Clinical Laboratory Summary Statistics: Clinical Chemistry (Safety Population)
14.3.3.2	Clinical Laboratory Shift Tables: Clinical Chemistry (Safety Population)
14.3.4.1	Clinical Laboratory Summary Statistics: Urinalysis (Safety Population)
14.3.4.2	Clinical Laboratory Shift Tables: Urinalysis (Safety Population)
14.3.5	Vital Signs Summary Statistics (Safety Population)
14.3.6	Prior and Concomitant Medications (Safety Population)

Listing No.	Data Listing Title
16.2.1	Subject Disposition and Off-Treatment Listing (All records)
16.2.2	Protocol Deviations Listing (Safety Population)
16.2.3	Patients Excluded from the Efficacy Analysis (Safety Population)
16.2.4.1	Subject Demographics Listing (Safety Population)
16.2.4.2	Medical History Listing (Safety Population)
16.2.4.3	Concomitant Medications Listing (Safety Population)
16.2.5.1	Treatment Compliance Listing (Safety Population)
16.2.5.2	Drug Concentration Data Listing (Safety Population)
16.2.6.1	Subject Primary Efficacy Variables Listing: COVID-19 Status, VRI Status (Safety Population)
16.2.6.2	Subject Secondary Efficacy Variables Listing: ARI Status, Hospitalization Status, Mortality (Safety Population)
16.2.6.3	SARS-CoV-2 Antibody Status (Safety Population)

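### The protocol enrols from age 55 but the SAP's age subgroups start at 65, so both primary-endpoint age tables would leave out any ITT subject aged 55 to 64

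*SAP*

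**What the plan says.** Protocol 4.1 sets the lower age limit: "Male and female residents of LTCFs at least 55 years of age". The protocol synopsis gives the same limit, and Appendix IV dates the change to Amendment 4, effective 26 August 2020.

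The SAP does not follow. Section 1.1 describes the residents as "aged 65 years and over". Section 2.2.2 defines the age subgroups as "age (65 to 79 years, 80 years and over", and section 4.2.1 gives the same two bands: "age (65- to 79 years or 80 years and over". The SAP's revision history lists no change to the age range.

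The ITT definition in SAP 2.2.1 depends on dosing and baseline virology, not on age: "the ITT population includes all patients in the safety population who did not have a laboratory detected respiratory virus infection at the baseline visit". SAP 8.0 plans the age tables on that population. Table 14.2.1.9 is titled "Cochran-Mantel-Haenszel Test Results by Age Group: Symptomatic COVID-19 Subject Status (ITT Population", and Table 14.2.1.10 is its counterpart for VRI.

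**The concern.** A resident aged 55 to 64 who is randomized, dosed and free of respiratory virus at baseline belongs to ITT and counts in the primary tests, but fits neither age band. The age tables are labelled as ITT tables, yet would silently restrict ITT to ages 65 and over.

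Age is one of only three subgroup factors planned for the primary endpoints. The sex and race categories cover the whole population; the age categories do not. The band left out is the one that the current protocol admits and the SAP does not describe. If the gap were noticed only after unblinding, any age group added to close it would not be pre-specified.

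**Working it through.** **Age coverage.** Setting the texts side by side:

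- Eligible (Protocol 4.1): 55 and over.
- In ITT (SAP 2.2.1): any eligible age.
- Assigned to a subgroup (SAP 2.2.2 and 4.2.1): 65-79 together with 80+, that is, 65 and over.
- Not assigned: 55, 56, ..., 64, which is ten whole years of age.

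This result needs no assumption.

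**Expected cases.** SAP 1.3 assumes 400 subjects per arm, with rates of 5% against 1% for COVID-19 and 10% against 2% for VRI.

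- COVID-19: 400 × 0.05 + 400 × 0.01 = 24, which reproduces the 24 events in SAP 2.4. As a share, 24/800 = 3%.
- VRI: 400 × 0.10 + 400 × 0.02 = 48, or 48/800 = 6%.

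**Possible size of the omission.** The documents do not say how many subjects were aged 55 to 64, so the following is illustrative. Assumptions:

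- The earlier limit was 65, as SAP 1.1 suggests, so only subjects enrolled after 26 August 2020 can be in the band.
- Accrual of the 800 is even.
- Last enrolment is 8 weeks before the planned end of the study: 31 December − 56 days = 5 November 2020.
- 10-30% of later enrolees are aged 55 to 64.
- Risk is the same at all ages, and all 800 are in ITT.

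Later enrolees = 800 × (days from the age change to 5 November) / (days from first enrolment to 5 November). Subjects in the band = later enrolees × share. Expected cases = subjects × 3% or 6%.

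| Scenario | Days | Later enrolees | Share 55-64 | Subjects | COVID-19 cases | VRI cases |
|---|---|---|---|---|---|---|
| Low: 1 April start, 28 days for IRB approval | 43/218 = 19.7% | 158 | 10% | 16 | 0.5 | 0.9 |
| Base: 1 April start, no delay | 71/218 = 32.6% | 261 | 10-30% | 26-78 | 0.8-2.3 | 1.6-4.7 |
| High: 30 April start, no delay | 71/189 = 37.6% | 301 | 30% | 90 | 2.7 | 5.4 |

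From low to high, the omitted share is 16/800 = 2% to 90/800 = 11% of subjects and, with equal risk, of expected cases. The enrolment pause at the first interim review (Protocol 14) and exclusions for infection at baseline are not modelled.

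One scaling figure is free of the calendar assumptions: each 10% of ITT in the band removes 80 subjects, 80 × 3% = 2.4 expected COVID-19 cases and 80 × 6% = 4.8 expected VRI cases.

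**The case against.** The case for leaving this alone is that little depends on it. The age analyses carry no alpha and no decision rule. With 24 COVID-19 cases expected, and a test stratified by up to 20 facilities, age-group results would be imprecise even with complete bands. Results for 65-79 and 80+ remain valid for those ages. All of this stands, and it is why the point is minor.

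The gap would also not be hidden. If the age tables show counts, adding the two bands and comparing the sum with Tables 14.2.1.1 and 14.2.1.2 exposes the shortfall. SAP 3.0 reports the minimum age ("Continuous variables (age, baseline height, baseline weight) will be summarized via mean, standard deviation, minimum"), and Listing 16.2.4.1 ("Subject Demographics Listing (Safety Population") with Listing 16.2.6.1 gives age and case status by subject. That stands too, but being able to detect the omission after the event does not supply a pre-specified group.

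The size estimate is the weakest part. The 10-30% share has no source in the documents, the first-enrolment date is not given, and the 7-day window on the Week 8 visit is ignored. Starting on 17 May, the date of protocol version 3.0, gives 71/172 = 41.3%, or about 330 later enrolees and up to 99 subjects (3.0 COVID-19 and 5.9 VRI cases). So 16 to 90 is a range of scenarios, not a bound, and zero remains possible. None of this bears on the mismatch itself, which does not depend on the count.

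**Conclusion.** The concern holds, as a minor point and with high confidence in the mismatch. The SAP's age bands do not cover the population that the current protocol enrols, and no rule in the SAP repairs this. Two supportive tables would be incomplete if even one ITT subject is aged 55 to 64. How many are affected is unknown and may be none; 2-11% of subjects and expected cases is an illustration that rests on the assumed age share, even accrual, the assumed enrolment dates and equal risk across ages. The primary comparisons, their alpha and power, the sex and race subgroups and the safety analyses do not use the age bands, so the primary conclusions do not change.

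**What to change.** Before unblinding:

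- Change the population in SAP 1.1 to 55 years and over.
- Redefine the age groups in SAP 2.2.2 and 4.2.1 so that every ITT subject falls in exactly one. Either 55-64, 65-79 and 80+, or 55-79 and 80+ if blinded counts show that the youngest band is sparse. Both keep the existing cut at 80.

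What the documents require is complete coverage; the choice between the two groupings is a matter of judgement, to be settled on blinded counts and recorded in the SAP.

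The cost is three SAP lines and at most one extra group in each of two tables. With three groups, the youngest may hold very few events (about 0.5 to 2.7 expected COVID-19 cases in the scenarios tabulated above). With two groups, there is no separate result for ages 55 to 64.
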